2.4.7 Analyses of ADA variables

The baseline value used to define ADA variables is the original baseline from the parent studies. The ADA analyses will be performed on the ADA population (Section 2.3.5). The ADA variables described in Section 2.1.6 will be summarized using descriptive statistics in the ADA analysis set. Frequency tables of the proportion of patients developing ADA positivity in the ADA assay, neutralizing antibody status in the NAb assay, pre-existing immunoreactivity, treatment-emergent, treatment-boosted, persistent, indeterminate, transient ADA responses and titers will be presented. Listing of all ADA peak titer levels and neutralizing antibody status will be provided for ADA positive patients.

2.4.7.1 Status in the ADA assay at baseline of the parent study

The following summary will be provided based on the ADA population (Section 2.3.5):

- Number (%) of patients negative in the ADA assay at baseline of parent study
- Number (%) of patients positive in the ADA assay at baseline of parent study
 - The summary statistics (including number, median, Q1, Q3, minimum and maximum) of the titer for the patients positive in the ADA assay at baseline of the parent study
 - Number (%) of patients with neutralizing antibody status (negative or positive in the NAb assay)

2.4.7.2 Status in the ADA assay in the current study

The following summary will be provided based on ADA population (Section 2.3.5):

- Number (%) of patients with ADA status (negative or positive in the ADA assay) at time points analyzed
 - The summary statistics (including number, median, Q1, Q3, minimum and maximum) of the peak post-baseline titer for ADA positive patients

- ADA titers using descriptive statistics (median, Q1, Q3, minimum and maximum) at ADA time points analyzed
- Number (%) of patients with neutralizing antibody status (negative or positive in the NAb assay) for the ADA positive patients
- Number (%) of patients with pre-existing immunoreactivity
- Number (%) of patients with treatment-boosted anti-drug antibodies.
 - The summary statistics (including number, median, Q1, Q3, minimum and maximum) of the peak post-baseline titer for treatment-boosted ADA patients
- Number (%) of patients with treatment-emergent ADA.
 - The summary statistics (including number, median, Q1, Q3, minimum and maximum) of the peak post-baseline titer for treatment-emergent positive patients
 - Number (%) of patients in the low, moderate or high titer category with treatmentemergent positive response
 - Number (%) of patients with transient, indeterminate, or persistent treatment-emergent ADA response
- Number (%) of patients with neutralizing antibody results (negative or positive in the NAb assay).

2.4.7.3 Impact of ADA on clinical safety

The safety assessment will focus on the following events:

- Severe injection site reactions last longer than 24 hours or serious injection site reactions
- Hypersensitivity reactions (SMQ hypersensitivity narrow search and confirmed by medical review)
- Anaphylactic reactions (SMQ anaphylactic reaction narrow search)

In response to AE's of special interest like anaphylaxis or hypersensitivity additional ADA samples closer to the event may be analyzed, based on the judgment of the medical investigator and/or medical monitor.

Correlations between ADA variables (eg, ADA peak titers, neutralizing antibody status, treatmentemergent, treatment-boosted, transient, indeterminate and persistent ADA responses) and safety may be explored.

2.4.7.4 Impact of ADA on clinical efficacy

Correlations between ADA variables (eg, ADA peak titers, neutralizing antibody status, treatmentemergent, treatment-boosted, transient, indeterminate and persistent ADA responses) and efficacy endpoints may be explored for each treatment category and overall (see Section 2.3.2):

- Annualized rate of severe exacerbation events
- Change from baseline in FEV1

2.4.7.5 Impact of ADA on PK

Correlations between ADA variables (eg, ADA peak titers, neutralizing antibody status) and descriptive summary of serum concentration of dupilumab may be explored for each treatment category and overall (see Section 2.3.2). Plot of individual serum concentration of functional dupilumab over visits may also be provided by ADA classifications (negative at all time, pre-existing immunoreactivity, treatment-boosted anti-drug antibodies, and treatment-emergent anti-drug antibodies [further separated by NAb status and peak titer category]) for each treatment category and overall (see Section 2.3.2).

2.5 DATA HANDLING CONVENTIONS

2.5.1 General conventions

The following formulas will be used for computation of parameters.

Demographic formulas

Age is calculated as following:

```
Age = integer part of (informed consent date – birth date)/365.25
```

Age of onset of asthma is calculated as following:

```
Age = integer part of (asthma onset date - birth date)/365.25
```

BMI is calculated as following:

```
BMI = Weight in kg / (height in meters)
```

Smoking quantity (pack-year) is calculated as following:

Number of pack-year= (packs smoked per day) × (years as a smoker)

Renal function formulas

Creatinine clearance (CLcr) value will be derived using the equation of Cockroft and Gault:

CLcr (ml/min) = (140 - age) * weight (kg) * (1 - 0.15*sex (0-M, 1-F)) /(0.814*creatinine (μ mol/l))

CLcr will be calculated using weight assessed at the same visit that creatinine was assessed and age at the lab sampling date. Here age is calculated as following:

Age = integer part of (lab sampling date – birth date)/365.25

2.5.2 Data handling conventions for secondary efficacy variables

Calculation of salbutamol/albuterol or levosalbutamol/levalbuterol inhalations/day:

A diary day is defined as the period beginning with an Evening diary, and ending with the following day's Morning Diary. The number of salbutamol/albuterol or levosalbutamol/levalbuterol inhalations per day is the sum of number of inhalations recorded in one diary day including the evening diary and the following day's morning diary.

Periodical average of daily efficacy endpoints at designated study days:

For the daily efficacy endpoints, the time period used to calculate the periodical average at each designated study day is summarized in Table 4. The day of the first IMP administration in LTS12551 study is used as the reference start day (day 1). The use of electronic diary and PEF meter will be stopped after the approval of protocol amendment 4, the periodical average calculation will be performed to the data observed within each interval up to the end of using electronic diary/PEF meter in LTS12551.

		Day 15	Day 29	Day 57	Day 85	Day 169	Day 337	Day 505
	Endpoint			Days use	d to comp	ute average	9	
Days used to compute average	morning PEF, asthma symptom score, number of awakenings	2-15	16-29	30-57	58-85	86-169	170-337	338-505
	evening PEF, asthma symptom score	1-14	15-28	29-56	57-84	85-168	169-336	337-504
	Number of inhalations/day of salbutamol/albuterol or levosalbutamol/levalbuterol for symptom relief	Diary day ^a 1-14	Diary day 15-28	Diary day 29-56	Dairy day 57-84	Diary day 85-168	Diary day 169-336	Diary day 337-504

Table 4 - Periodical average of daily efficacy assessment

a Note: A diary day is defined as the period beginning with an Evening diary, and ending with the following day's Morning Diary. For example, diary day 14 includes the evening dairy on day 14 and the morning dairy on day 15

		Day 589	Day 673			
Endpoint		Days used to compute average				
Days used to compute average	morning PEF, asthma symptom score, number of awakenings	506-589	590-673			
	evening PEF, asthma symptom score	505-588	589-672			
	Number of inhalations/day of salbutamol/albuterol or levosalbutamol/levalbuterol for symptom relief	Diary dayª 505-588	Diary day 589-672			

a Note: A diary day is defined as the period beginning with an Evening diary, and ending with the following day's Morning Diary. For example, diary day 14 includes the evening dairy on day 14 and the morning dairy on day 15

2.5.3 Missing data

For categorical variables, patients with missing data are not included in calculations of percentages unless otherwise specified. When relevant, the number of patients with missing data is presented.

Handling of computation of treatment duration if investigational medicinal product end of treatment date is missing

For the calculation of the treatment duration, the date of the last dose of IMP is equal to the date of last administration reported on the end-of-treatment case report form page. If this date is missing, the exposure duration should be left as missing.

The last dose intake should be clearly identified in the case report form and should not be approximated by the last returned package date.

Handling of medication missing/partial dates

No imputation of medication start/end dates or times will be performed. If a medication date or time is missing or partially missing and it cannot be determined whether it was taken prior or concomitantly, it will be considered a prior and concomitant medication.

Handling of adverse events with missing or partial date/time of onset

Missing or partial adverse event onset dates and times will be imputed so that if the partial adverse event onset date/time information does not indicate that the adverse event started prior to treatment or after the treatment-emergent adverse event period, the adverse event will be classified as treatment-emergent. No imputation of adverse event end dates/times will be performed. These data imputations are for categorization purpose only and will not be used in listings. No imputation is planned for date/time of adverse event resolution.

Handling of adverse events when date and time of first investigational medicinal product administration is missing

When the date and time of the first IMP administration is missing, all adverse events that occurred on or after the day of randomization should be considered as treatment-emergent adverse events. The exposure duration should be kept as missing.

The last dose intake should be clearly identified in the case report form and should not be approximated by the last returned package date.

Handling of missing assessment of relationship of adverse events to investigational medicinal product

If the assessment of the relationship to IMP is missing, then the relationship to IMP has to be assumed and the adverse event considered as such in the frequency tables of possibly related adverse events, but no imputation should be done at the data level.

Handling of missing severity/grades of adverse events

If the severity/grade is missing for 1 of the treatment-emergent occurrences of an adverse event, the maximal severity on the remaining occurrences will be considered. If the severity is missing for all the occurrences, a "missing" category will be added in the summary table.

Handling of potentially clinically significant abnormalities

If a patient has a missing baseline he will be grouped in the category "normal/missing at baseline."

For PCSAs with 2 conditions, one based on a change from baseline value or a normal range and the other on a threshold value, with the first condition being missing, the PCSA will be based only on the second condition.

For a PCSA defined on a threshold and/or a normal range, this PCSA will be derived using this threshold if the normal range is missing; eg, for eosinophils the PCSA is > 0.5 GIGA/L or >ULN if ULN \geq 0.5 GIGA/L. When ULN is missing, the value 0.5 should be used.

Measurements flagged as invalid by the laboratory will not be summarized or taken into account in the computation of PCSA values.

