8.1.3 Dose schedule

The IMP is administered every 14±3 days (q2w). The consecutive doses of the IMP must be separated by ≥11 days to avoid an overdose. Reminder: Patients will be monitored for any signs or symptoms of hypersensitivity reactions for a minimum of 30 minutes after IMP injection.

At the Enrollment (Combined V1/V2) Visit, the Investigator or delegate will train the patient (and/or caregiver[s]) how to prepare and inject IMP for the first injection or if the patient is already self-injecting (in the parent study), the Investigator or delegate will supervise the self-injection.

For subsequent doses, which are not given at the study site, specific pages will be provided to the patients to record information related to the injections. The pages will be kept as source data in the patient's study file.

If the patient (or caregiver) is unable or unwilling to administer IMP, arrangements must be made for qualified site personnel and/or healthcare professionals (eg, visiting nurse service) to administer IMP for the doses that are not scheduled to be given at the study site.

If the study visit is not performed at the study site as scheduled, the dose will be administered by the patient and/or their caregiver/healthcare professional, or arrangements must be made for a visit to the site to administer the IMP.

When IMP is administered at home, the patients must be advised by the site staff, to self-monitor for at least 30 minutes after administration for potential signs and symptoms that may suggest a hypersensitivity reaction.

Subcutaneous injection sites should be alternated between the 4 quadrants of the abdomen (avoiding navel and waist areas), the upper thighs, or upper arms (lateral side), so that the same site is not injected twice consecutively. Injection in the upper arms could be done only by a trained person (parent/caregiver trained by Investigator or delegate) or health care professional but not the patient themselves. For each injection, the anatomic site of administration will be recorded in the electronic case report form (e-CRF) and, as applicable, the home dosing diary.

Detailed instructions for transport, storage, preparation, and administration of IMP are provided to the patient.

Patients will complete a home dosing diary to document compliance with self-injection (or parent or caregiver injection) of IMP.

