10.3.5 Procedure and consequence for patient withdrawal from study

The patients may withdraw from the study before study completion if they decide to do so, at any time and irrespective of the reason.

For patients who fail to return to the study site, the Investigator should make the best effort to re-contact the patient (eg, contacting patient's family or private physician, reviewing available registries or health care databases), and to determine his/her health status, including at least his/her vital status. Attempts to contact such patients must be documented in the patient's records (eg, times and dates of attempted telephone contact, receipt for sending a registered letter).

If possible, the patients are assessed using the procedures normally planned for the EOT Visit, including a PK sample, if appropriate.

A patient should only be designated as lost to follow-up if the site is unable to establish contact with the patient after 3 documented attempts via 2 different methods (phone, text, e-mail, certified letter, etc).

Patients who have withdrawn from the study cannot be re-enrolled (treated) in the study. Their inclusion and treatment numbers must not be reused. The statistical analysis plan (SAP) will specify how these patients lost to follow-up for their primary endpoints will be analyzed. The patients may withdraw from the study before study completion if they decide to do so, at any time and irrespective of the reason.

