2.4.3.1 Extent of investigational medicinal product exposure

The extent of IMP exposure will be assessed by the duration of IMP exposure in LTS12551 study.

Duration of investigational product exposure is defined as: the last IMP dose date in LTS12551 study – the first IMP dose date in LTS12551 study + 14 days, regardless of unplanned intermittent discontinuations (see Section 2.5.3 for calculation in case of missing or incomplete data).

Duration of IMP exposure will be summarized descriptively as a quantitative variable (number, mean, SD, median, minimum, and maximum). In addition, duration of treatment exposure will also be summarized categorically by counts and percentages for each of the following categories and cumulatively according to these categories (the categories exceeding Week 48 may apply to only the patients on the 96-week treatment period who signed the informed consent form before the approval of protocol amendment 4):

 \leq 4 week

- > 4 and \leq 12 weeks
- > 12 and ≤ 24 weeks
- > 24 and ≤ 48 weeks
- > 48 and \leq 72 weeks
- > 72 and \leq 96 weeks
- >96 weeks

Additionally, the cumulative duration of treatment exposure, will be provided in patient years by treatment category and overall (see Section 2.3.2).

Number and percentage of patients will be summarized by total number of injections they received during the LTS12551 study. The number and percentage of patients who receive injection will be summarized by type of administrator (site staff, patient or non-professional care giver, professional care giver at home), by dosing week, and maybe by IMP packaging way (vial or pre-filled syringe).

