2.4.5.1 Analyses of adverse events

Generalities

The primary endpoint of this study is the number (n) and percentage (%) of patients experiencing any treatment-emergent adverse events (TEAE). Pre-treatment (if applicable) adverse events will be described separately.

If an adverse event date/time of onset (occurrence, worsening, or becoming serious) is incomplete, an imputation algorithm will be used to classify the adverse event as pre-treatment or treatmentemergent adverse event. The algorithm for imputing date/time of onset will be conservative and will classify an adverse event as treatment-emergent, unless there is definitive information to determine it is pre-treatment. Details on classification of adverse events with missing or partial onset dates are provided in Section 2.5.

Adverse event incidence tables will be presented by system organ class (SOC), high level group term (HLGT), high level term (HLT) and preferred term (PT) sorted in alphabetical order, to summarize the number (n) and percentage (%) of patients experiencing at least an AE by the treatment category and overall (see Section 2.3.2). Multiple occurrences of the same event in the same patient will be counted only once in the tables within a treatment category. The denominator for computation of percentages is the safety population within each treatment category. In all AE incidence tables, the total patient years (in the unit of 100 patient-years) for each treatment category and overall (see Section 2.3.2) will be presented in the corresponding column headers.

The number of events per 100 patient-years (adjusted for the total duration of exposure) by the treatment category and overall (see Section 2.3.2) will be presented for each AESI during the treatment-emergent period.

The table of all treatment-emergent adverse events presented by SOC and PT will be sorted by the internationally agreed SOC order (from MedDRA) and decreasing frequency of PTs within SOCs. Sorting will be based on the results for the overall patients across treatment categories, unless otherwise specified.

Analysis of all treatment-emergent adverse events

The following treatment-emergent adverse event summaries by the treatment category and overall patients (see Section 2.3.2) will be generated for the safety population. Sorting will be based on the results for the overall patients across treatment categories, unless otherwise specified.

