3 INTERIM ANALYSIS

This is an open-label extension study. Interim analyses/reports may be prepared to support regulatory submission of an indication in the dupilumab project or other purpose.

Interim analysis for non-asthma submission

In general, the analyses for this report will focus on the safety evaluations on the accumulative data in LTS12551 as of the cut-off date. Specifically, the report shall include all safety analyses, demographics, baseline characteristics, patient disposition, exposure to IMP, as well as the prior and concomitant medications.

Interim analysis for asthma submission

All planned analyses in this SAP shall be performed for this report.

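### SAP 2.5.3 leaves exposure missing when the end-of-treatment CRF page has no last-dose date, has no fallback to recorded injections, and gives no rule for patients still on treatment at an interim lock

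*SAP*

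**What the plan says.** SAP 2.4.3.1 defines exposure as last dose minus first dose plus 14 days and refers to SAP 2.5.3 for missing data. There, "the date of the last dose of IMP is equal to the date of last administration reported on the end-of-treatment case report form page"; and "If this date is missing, the exposure duration should be left as missing". The only proxy mentioned is ruled out: the last dose "should not be approximated by the last returned package date".

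Three results use this date.

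- **AESI and AE-grouping rates.** SAP 2.4.5.1 plans "The number of events per 100 patient-years (adjusted for the total duration of exposure", and total patient-years stand in the column headers of the AE incidence tables.
- **Severe exacerbations.** In SAP 2.1.3.1 both the event window and the duration end at last dose plus 14 days.
- **Visit windows.** In SAP Tables 5 to 7, d* is the later of last dose plus 14 days and the EOT date. It bounds only the EOT and EOS rows.

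For the asthma-submission interim report, SAP 3 says "All planned analyses in this SAP shall be performed for this report", and SAP 4 schedules an interim lock at the initial asthma application. Neither section gives an exposure rule for patients still being dosed.

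On data capture, Protocol 8.1.3 says "For each injection, the anatomic site of administration will be recorded in the electronic case report form (e-CRF". Protocol 8.7.1 has the monitor check an IMP administration page, and Protocol 10.3.1 has missed injections recorded on the e-CRF IMP pages.

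**The concern.** A rate per patient-year is valid only if numerator and denominator cover the same people over the same time. The rule removes time from the denominator, and nothing in the SAP removes the matching AESI or AE-grouping events. SAP 2.5.3 accepts this imbalance openly in a neighbouring case: when the first-dose date is missing, adverse events from the day of randomisation onward count as treatment-emergent and exposure stays missing.

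The loss of time is also not random. It depends on how, or whether, treatment has ended. At final lock that means patients whose treatment ended without a completed form. At an interim lock it could mean everyone still on treatment. At stake are the exposure-adjusted safety rates of a study whose primary objective is long-term safety, including those in a marketing application.

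**Working it through.** The documents state no patient-years, event rates or shares with a missing date, so there is no figure of the plan's own to reproduce. The shares below are assumptions.

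**Formula for AESI and AE-grouping rates.** Let d be the share of patients without a last-dose date, f their mean exposure relative to the others, T the others' mean exposure and λ a common event rate. Events are proportional to λ[(1−d)T + d·f·T]; counted time is (1−d)T. Hence reported rate / true rate = 1 + d·f/(1−d).

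**Final lock**

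| d | f = 0.5 | f = 1 |
|---|---|---|
| 2% | 1 + 0.010/0.98 = 1.010 | 1.020 |
| 5% | 1 + 0.025/0.95 = 1.026 | 1.053 |
| 10% | 1 + 0.050/0.90 = 1.056 | 1.111 |

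**Interim lock, literal reading** (ongoing patients' events kept, their time dropped). With share q ongoing and equal mean exposure, the ratio is 1/(1−q): 1.33 at 25%, 2.0 at 50%, 4.0 at 75%.

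The answer also depends on how much exposure the finished patients have. Take a mean of 0.5 years for ongoing patients:

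| Mean exposure of finished patients | q = 50% | q = 80% |
|---|---|---|
| 0.9 years (near 48 weeks: 336/365.25 = 0.92) | 0.70/0.45 = 1.56 | 0.58/0.18 = 3.22 |
| 1.84 years (96 weeks: 672/365.25) | 1.17/0.92 = 1.27 | 0.768/0.368 = 2.09 |

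The share ongoing could be large. SAP 1.5 dates the approval of Amendment 4 at 31 October 2016. A patient enrolled after it reaches Week 48 (336 days) no earlier than about 2 October 2017, later than this SAP (20 July 2017). The lock date itself is not given.

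**Severe exacerbations.** Events and time both need the missing date. If both are dropped, the ratio is 1 at a common rate. If the dropped patients' true rate is k times that of the others, reported/true = [(1−d) + d·f] / [(1−d) + d·f·k]. At d = 10% and f = 0.5 this is 0.95/1.00 = 0.95 for k = 2 and 0.95/1.05 = 0.905 for k = 3. Any bias is therefore towards understatement when those who disappear are sicker.

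**Primary endpoint.** SAP 2.4.5.1 uses the safety population as denominator for percentages. Exposure does not enter.

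**Is another source available?** The e-CRF holds injection records, as cited above. The documents do not list the fields on those pages, but SAP 2.4.3.1 plans injection summaries by dosing week, which needs their timing. Only the returned-package date is barred.

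**How current are those records at a cut-off?** After Week 24, visits are 12 weeks apart (Protocol 1.2 and 1.3), and home injection sheets come back at visits (Protocol 8.7.1). Just before a visit, the last recorded dose may be nearly 12 weeks old. Adding 14 days still leaves about 10 weeks and up to five home doses uncounted, while monthly telephone calls continue to collect safety information.

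**The case against.** The best defence has four parts.

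1. **A form is not a visit.** SAP 2.5.3 needs a date on a page. Protocol 10.3 requires any IMP discontinuation to be documented in the e-CRF, and Protocol 10.3.4 requires permanent discontinuations to be recorded. The wording "If possible, the patients are assessed using the procedures normally planned for the EOT Visit" in Protocol 10.3.5 concerns EOT procedures. This stands. A reader might infer that lost and withdrawn patients as a class have no last-dose date; the documents do not support that. Only patients whose date is actually absent are affected.
2. **The numerator is read more generously than the denominator.** The default to treatment-emergent in SAP 2.5.3 concerns incomplete AE onset dates, and the treatment epoch in SAP 2.1.4 also closes at last dose plus 14 days. This stands in part: counting these patients' events is an inference. But no text excludes them, and the missing-first-dose rule shows the SAP counting events without time.
3. **Exacerbation rates are not inflated.** Correct. A reader might carry over the idea of events without time, but both parts of that rate are undefined together.
4. **The interim problem comes from silence.** For an ongoing patient the date is not yet due rather than missing, and SAP 3 speaks of data as of a cut-off, so last dose as of the cut-off is a natural reading. This stands against presenting any interim inflation as the plan's stated result. It does not supply a rule, and that reading would still meet the recording lag shown above.

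It is also fair to add that the study is descriptive and plans no systematic testing.

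**Conclusion.** The concern holds for the exposure-based results. SAP 2.5.3 is explicit that a missing end-of-treatment date makes exposure missing, although a better source is already collected. For affected patients, AESI and AE-grouping rates can gain events without time, exacerbation count and time are both undefined, and d* cannot be evaluated as written for the EOT and EOS windows. The number and percentage with any treatment-emergent event do not change.

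At final lock the overstatement is about 1 to 3%, if 2 to 5% lack the date and had half the others' exposure. At the interim lock the gap matters more, but its size is open. The figures of 1.27 to 3.22 illustrate one literal reading under assumed shares and exposures; they are neither bounds nor predictions. Reading them as what the sponsor will report would go beyond the documents.

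**What to change.** Amend SAP 2.5.3 and refer to it from SAP 3:

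- If the end-of-treatment page has no last-dose date, use the latest injection date on the e-CRF IMP administration page. Leave exposure missing only if no injection is recorded, and report how many patients that is.
- For patients ongoing at an interim cut-off, count exposure to the cut-off date. Last recorded injection plus 14 days is not a good substitute because of the lag in home-injection records.
- Apply the same end date to the treatment-emergent period, the exacerbation count and time, and d*, so that events and person-time match.

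The cost is a few sentences of SAP text and one derivation from data already collected. Two downsides remain. For lost patients, a few unrecorded home doses may be missed. For ongoing patients, exposure may be slightly overstated where someone has stopped and this is not yet recorded.
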